4.1 Inclusion criteria

- Cognitively intact healthy controls will be recruited from an ongoing community-recruited longitudinal cohort of cognitively intact older adults (55-85 years, S51125) who all have undergone amyloid PET at the baseline visit in the context of study S51125. Half of the subjects will be amyloid-positive and half will be amyloid-negative. In the context of study S51125 these subjects receive two-yearly neuropsychological assessment.
- MCI patients (Petersen et al., 2004 criteria) will be recruited from an ongoing memory-clinic recruited longitudinal cohort of patients with amnestic mild cognitive impairment who participate in study S55892. All subjects have undergone an amyloid PET at the baseline study in the context of study S55892. Half of the subjects will be amyloid-positive and half will be amyloid negative.
- Clinically probable AD subjects (NINCDS-AIREN criteria) will be recruited from the memory clinic UZ Leuven (MMSE 12-28). Subjects will be recruited only if they are capable of providing written informed consent.
- Clinically probable LBD (McKeith et al. criteria, 2005) will be recruited from the memory clinic UZ Leuven (MMSE 12-28). Subjects will be recruited only if they are capable of providing written informed consent.
- Capable and willing to participate

4.2 Exclusion criteria

- Personal medical history of retinal neovascularization
- Unable or unwilling to give consent

4.3 Expected duration of trial

10 minutes per person

5. Trial Procedures

1. Informed consent: AD en LDB patients will be accompanied by a personal study partner who will verify and sign whether the purpose, course and voluntary nature of the trial has been explained to the patient in a clear and understandable language, prior to signing the informed consent.

2. Medical questionnaire assessing personal medical history of cardiovascular diseases and cardiovascular risk factors. When necessary, the Electronic Health Record as well as treating physicians might be consulted to complete the questionnaire.
3. Basic non-invasive ophthalmic examination: visual acuity, slit lamp assessment of the anterior and posterior segments, lens grading and non-dilated fundus photography
4. OCT: Macula centered cube followed by optic disc centered cube, for both eyes
Each scan takes approximately 2.5 seconds.
5. Retinal and choroidal thickness and motion decorrelation will be measured using the provided software.
6. The diagnostic performance of these OCT parameters to classify between amyloid positive vs amyloid negative controls, amyloid-positive vs amyloid negative MCI, AD and DLBD will be evaluated.

6. Assessment of efficacy

/

7. Assessment of Safety

The power and frequency of the light source used by the fundus camera and by the spectral-domain OCT are completely harmless for the human retina and cause no subjective discomfort. The OCT device uses a faint light at the near-infrared spectrum that can barely be perceived by the human eye. Pupillary dilatation is not required.

8. Statistics

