8.1 Sample size

As of now, there is no data available on the distribution of flow index or vessel density in the population. This exploratory study is aimed to provide data on the distribution of these parameters in the healthy and diseased population. For this purpose, we will recruit 15 amyloid-positive and 15 amyloid-negative cognitively intact controls, 15 amyloid-positive and 15 amyloid-negative MCI, 15 clinically probable AD in an early stage and 10 clinically probable LBD.

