8.2 Analysis

Demographics and measured parameters will be analyzed with descriptive statistics (mean \pm standard deviation). Image analysis for the OCT will be performed with the software provided by the manufacturer. To evaluate the diagnostic performance of these parameters in distinguishing between subcategories, 'receiver operating characteristic' (ROC) curves with 'area under the curve' (AUC) analysis will be used. Logistic regression models will be used to assess the association between retinal/choroidal vascular parameters and cardiovascular risk factors. Statistical significance will be based on two-sided P-values of <0.05 . All statistical analyses will be performed using SPSS 20.0 for Mac (SPSS Inc., Chicago, IL, USA).

9. Quality assurance

To assure maximal quality and reproducibility, the trial protocol will be followed rigorously.

10. Direct access to source data and documents

Demographics and disease-related parameters (functional assessment, biochemistry and imaging) will be retrieved from the electronic medical health record. When not available, additional tests will not be performed.

11. Ethics and regulatory approvals

The trial will be conducted in compliance with the principles of the Declaration of Helsinki (2008), the principles of GCP and in accordance with all applicable regulatory requirements. This protocol and related documents will be submitted for review to Ethics Committee of the University Hospitals Leuven.

The Study will be conducted only on the basis of prior informed consent by the Subjects to participate in the Study. We shall obtain a signed informed consent form (ICF) for all patients prior to their enrollment and participation in the Study in compliance with all applicable laws,

regulations and the approval of the (local) Ethics Committee, if required. We shall retain such ICFs in accordance with the requirements of all applicable regulatory agencies and laws.

12. Data Handling

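### Does scanning both eyes of each participant make the ROC and logistic analyses in section 8.2 invalid?

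*Protocol*

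**What the plan says.** Section 5, step 4, sets the imaging: "OCT: Macula centered cube followed by optic disc centered cube, for both eyes". Steps 5 and 6 then have thickness and motion decorrelation measured and their diagnostic performance assessed, "to classify between amyloid positive vs amyloid negative controls, amyloid-positive vs amyloid negative MCI, AD and DLBD will be evaluated".

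Section 8.2 gives the methods. For diagnostic performance, "receiver operating characteristic' (ROC) curves with 'area under the curve' (AUC) analysis will be used". For the vascular risk question, "Logistic regression models will be used to assess the association between retinal/choroidal vascular parameters and cardiovascular risk factors". The threshold is "Statistical significance will be based on two-sided P-values of <0.05". The section does not mention the unit of analysis, the choice of an eye, averaging or clustering. It does not mention confidence intervals either.

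Section 8.1 counts people: "15 amyloid-positive and 15 amyloid-negative cognitively intact controls, 15 amyloid-positive and 15 amyloid-negative MCI, 15 clinically probable AD in an early stage and 10" with LBD. The synopsis gives the total as 85. Section 8.1 also explains that the study is exploratory and has no power calculation, because "there is no data available on the distribution of flow index or vessel density in the population".

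**The concern.** Eighty-five people with two eyes each give up to 170 eye-level measurements per parameter. ROC/AUC and logistic regression in their usual form treat every row as independent. Amyloid status, diagnosis and cardiovascular risk factors are attributes of the person, so both eyes always carry the same label. If the eyes also resemble each other, the second eye adds only part of an independent observation.

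A spreadsheet with one row per eye, run through standard software, would overstate the precision. With groups of 10 to 15 people, that could turn a chance difference into an apparent diagnostic marker. Since section 8.2 has no step that takes two eyes to one value, it is natural to ask whether its 5% threshold means what it says.

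**Working it through.** **The protocol's own figure.** 15 + 15 + 15 + 15 + 15 + 10 = 85, as in the synopsis. The total is a count of people. There is no power or precision target to reproduce.

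**Inputs.** Two eyes per person (section 5); groups of 15 or 10 people (section 8.1); two-sided 0.05 (section 8.2). The between-eye correlation ρ is not in the protocol. It is assumed here, over 0.3 to 0.9.

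**If eyes were pooled as independent.** With two eyes per person and a person-level label, the variance is understated by the design effect 1 + ρ. The true two-sided error of a nominal 5% test is 2 × [1 − Φ(1.96/√(1+ρ))], and naive intervals have 1/√(1+ρ) of the correct width. The simulation column is a rank (AUC) test at 15 vs 15 people, 10,000 runs, with no true difference.

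| ρ | Design effect | True error, formula | True error, simulated | Width ratio | Coverage of nominal 95% interval |
|---|---|---|---|---|---|
| 0.3 | 1.3 | 8.6% | 8.3% | 0.88 | 91% |
| 0.5 | 1.5 | 11.0% | 10.4% | 0.82 | 89% |
| 0.7 | 1.7 | 13.3% | 13.0% | 0.77 | 87% |
| 0.9 | 1.9 | 15.5% | 15.2% | 0.73 | 84% |

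At 15 vs 10 people the simulated error is 8.6% to 15.7%. Eye-level logistic regression on 85 people, with an assumed risk-factor prevalence of 0.5 and 2,000 runs, gives 10.8% at ρ = 0.5 and about 15% at ρ = 0.8 to 0.9.

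For an AUC of 0.70, the Hanley-McNeil half-width of a 95% interval is about 0.19 with 15 vs 15 people. It is about 0.13 if 30 vs 30 eyes are taken as independent.

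**If each person contributes one value.** Over the same range of ρ, the rank test at 15 vs 15 gives 4.6% to 5.3% with the two-eye mean and 4.8% to 5.5% with a single eye. Logistic regression on the two-eye mean gives 4.1% to 4.8%. These are close to the nominal 5%.

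**What a single eye costs.** The SD of the two-eye mean relative to one eye is √((1+ρ)/2). It is 0.87 at ρ = 0.5 and 0.97 at ρ = 0.9, so averaging lowers the SD by 13% to 3%. At ρ = 0.3 the ratio is 0.81, a reduction of 19%. Using one eye is therefore valid, with a modest loss of precision unless the eyes are only weakly correlated.

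**Which case does the protocol prescribe?** Section 5 says what is scanned, and scanning both eyes does not define the analysis row. Sections 5 and 8.2 speak of telling groups of people apart. The synopsis and section 8.1 count people. No sentence uses 170, counts eyes or calls for eye-level analysis. Person-level analysis is the reading that agrees with every number in the protocol.

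**The case for a change.** The strongest argument for a change is that a person-level reading still leaves a choice: right eye, left eye or mean. If that choice were made after seeing the data, the 5% level would suffer even without pooling. Simulations at 15 vs 15, taking the smallest P-value of the three options, give an error of about 7% to 10% for ρ between 0.9 and 0.5, for one parameter in one comparison. One sentence would close this off at no cost in data or visits.

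The arithmetic stands, and a rule fixed before the data are analysed is good practice. But it shows a risk in how the gap might be filled, not a fault in what is written. Fixing the eye rule is ordinary content of a statistical analysis plan, and its absence from a short protocol is not evidence that the rule does not exist.

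The stakes are also limited. The study is described as exploratory, and its primary objective is the distribution of the parameters. Diagnostic performance is a secondary objective, although the synopsis also lists it as the endpoint, so its P-values do matter to some degree.

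**Conclusion.** No change to the protocol follows. This is a gap that analysts fill sensibly: with one value per person they follow section 8.2 exactly and keep the error near 5%.

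The inflation to about 9% to 16% is real only if eyes are pooled without adjustment, which the protocol does not prescribe. Its size also rests on an assumed between-eye correlation of 0.3 to 0.9, applied alike to thickness, flow index and vessel density. It cannot be said that the stated 5% level fails. Nor are there stated AUC intervals to be wrong, since section 8.2 specifies none.

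The conclusion would differ if the statistical analysis plan, which is not at hand, called for eye-level rows in ordinary ROC or logistic analyses with no allowance for clustering.

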8.1 Sample size

As of now, there is no data available on the distribution of flow index or vessel density in the population. This exploratory study is aimed to provide data on the distribution of these parameters in the healthy and diseased population. For this purpose, we will recruit 15 amyloid-positive and 15 amyloid-negative cognitively intact controls, 15 amyloid-positive and 15 amyloid-negative MCI, 15 clinically probable AD in an early stage and 10 clinically probable LBD.

8.2 Analysis

Demographics and measured parameters will be analyzed with descriptive statistics (mean \pm standard deviation). Image analysis for the OCT will be performed with the software provided by the manufacturer. To evaluate the diagnostic performance of these parameters in distinguishing between subcategories, 'receiver operating characteristic' (ROC) curves with 'area under the curve' (AUC) analysis will be used. Logistic regression models will be used to assess the association between retinal/choroidal vascular parameters and cardiovascular risk factors. Statistical significance will be based on two-sided P-values of <0.05 . All statistical analyses will be performed using SPSS 20.0 for Mac (SPSS Inc., Chicago, IL, USA).

9. Quality assurance

To assure maximal quality and reproducibility, the trial protocol will be followed rigorously.

10. Direct access to source data and documents

Demographics and disease-related parameters (functional assessment, biochemistry and imaging) will be retrieved from the electronic medical health record. When not available, additional tests will not be performed.

11. Ethics and regulatory approvals

The trial will be conducted in compliance with the principles of the Declaration of Helsinki (2008), the principles of GCP and in accordance with all applicable regulatory requirements. This protocol and related documents will be submitted for review to Ethics Committee of the University Hospitals Leuven.

The Study will be conducted only on the basis of prior informed consent by the Subjects to participate in the Study. We shall obtain a signed informed consent form (ICF) for all patients prior to their enrollment and participation in the Study in compliance with all applicable laws,

regulations and the approval of the (local) Ethics Committee, if required. We shall retain such ICFs in accordance with the requirements of all applicable regulatory agencies and laws.

12. Data Handling

We shall treat all information and data as confidential and shall not disclose such information to any third parties or use such information for any purpose other than the performance of the Study. The collection, processing and disclosure of personal data, will comply with applicable personal data protection and the processing of personal data (Directive 95/46/EC and Belgian law of December 8, 1992 on the Protection of the Privacy in relation to the Processing of Personal Data). We will protect the data from disclosure outside the research according to the terms of the research protocol and the informed consent document. The subject's name or other identifiers will be stored separately from their research data and replaced with a unique code to create a new identity for the subject.

13. Data Management

Volunteers will be matched to an anonymous identifier. Data will be recorded electronically in a spreadsheet. Images will be exported and permanently removed from the diagnostic device.

14. Translational research

No biological material will be collected/shipped/stored/used for the study

15. Publication Policy

Any publication will be submitted to all co-authors and sponsors for review at least thirty (30) days prior to submission or disclosure. Sponsor shall have the right to delay the projected publication for a

period of up to three (3) months from the date of first submission to the Sponsor in order to enable the Sponsor to take steps to protect its intellectual property rights and know-how.

16. Insurance/Indemnity

In accordance with the Belgian Law relating to experiments on human persons dated May 7, 2004, Sponsor shall assume, even without fault, the responsibility of any damages incurred by a Study Patient and linked directly or indirectly to the participation to the Study, and shall provide compensation therefore through its insurance.

17. Financial Aspects

Volunteers will not be charged with the cost of the additional examinations.

No commercial interests to declare.

18. References

1. Patton, Niall, et al. "Retinal vascular image analysis as a potential screening tool for cerebrovascular disease: a rationale based on homology between cerebral and retinal microvasculatures." *Journal of anatomy* 206.4 (2005): 319-348.
2. Cheung, Carol Yim-lui, et al. "Microvascular network alterations in the retina of patients with Alzheimer's disease." *Alzheimer's & Dementia* 10.2 (2014): 135-142.

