Purpose of clinical trial	To explore the distribution of novel optical coherence tomography (OCT) parameters in patients with different subtypes of dementia, MCI patients with or without positive amyloid scan and cognitively intact older adults and to evaluate the diagnostic value of these parameters.
Primary objective	Relative distribution of retinal and choroidal thickness, flow index and vessel density in the different subpopulations.
Secondary objective (s)	
- Diagnostic performance of the aforementioned parameters to distinguish the different subpopulations.- The association between these parameters and the presence of cardiovascular risk factors.
Trial Design	Observational, cross-sectional
Endpoints	The diagnostic performance of retinal and choroidal thickness, flow index and vessel density to classify between amyloid positive vs amyloid negative

	controls, amyloid-positive vs amyloid negative MCI, AD and DLBD.
Sample Size	
85
 
 -15 amyloid-positive and 15 amyloid-negative cognitively intact controls (55-80 years) - 15 amyloid-positive and 15 amyloid-negative MCI patients - 15 patients in the dementia stage of AD - 10 patients with LBD
Summary of eligibility criteria	
Confirmed diagnosis of MCI, AD, LBD or absence of dementia (cfr 4.1 inclusion criteria)
 
Capable and willing to participate

Maximum duration of treatment of a Subject	/
Version and date of final protocol	V1.1 17-04-2016
Version and date of protocol amendments	

2. Background and rationale

Being a direct extension of the central nervous system and the only place in the human body where the vessels of the central circulation can be visualized directly, the eye provides a unique window to investigate the central circulatory system. Several studies have demonstrated that retinal blood vessels show structural and functional alterations in patients with dementia. These measurements are based on fundus pictures and are hence limited to the larger retinal vessels.

Until recently, intravenous injection of a contrast agent was necessary to visualize the retinal microvasculature in detail. While indispensable for the diagnosis of some ocular vascular diseases (arterial/venous occlusion, neovascularization,...) the invasiveness of fluorescein angiography (and the risk of an allergic reaction) limits its use as a screening tool to detect alterations in the microvascular network of the retina and choroid.

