Optical coherence tomography (OCT) is a non-invasive diagnostic tool capable of generating cross-sectional coupes of the retina and choroid. Novel algorithms allow to render a 3-dimensional model of the ocular microcirculation based merely on the motion contrast of the circulating blood. Since OCT is fast, easy to perform and completely non-invasive, this technique lends itself for screening purposes.

The proposed study aims to investigate whether retinal or choroidal vascular parameters measured using OCT could be useful to identify different subpopulations of cognitive intact, MCI and dementia patients.

Figure 1. OCT camera

[figure not shown]

Figure 2. OCT angiography

3. Trial objectives and Design

In this observational study, we aim to evaluate whether changes in the retinal and choroidal circulation, as assessed by OCT are correlated with the degree and subtype of dementia and with the presence or absence of a positive amyloid scan.

For this purpose, patients with established AD and LBD, as well as amyloid positive and amyloid negative MCI and aged matched cognitively intact patients will be included in this cross-sectional study.

4. Selection and withdrawal of subjects

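### Does naming logistic regression without an outcome or covariates leave the cardiovascular risk-factor analysis confounded by diagnosis?

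*Protocol*

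**What the plan says.** The synopsis lists as a secondary objective "The association between these parameters and the presence of cardiovascular risk factors". Section 5, item 2, says where the risk factors come from: "Medical questionnaire assessing personal medical history of cardiovascular diseases and cardiovascular risk factors". Section 8.2 gives the analysis in one sentence: "Logistic regression models will be used to assess the association between retinal/choroidal vascular parameters and cardiovascular risk factors". No other method is named for this objective. The sentence does not say which side is the outcome, whether covariates enter, or whether the six groups are pooled.

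Four other places bear on the point:
- Section 8.2 summarises the measured parameters by mean and standard deviation, so they are treated as continuous.
- Section 3 asks whether "changes in the retinal and choroidal circulation, as assessed by OCT are correlated with the degree and subtype of dementia".
- Section 4.1 has controls "recruited from an ongoing community-recruited longitudinal cohort of cognitively intact older adults", and MCI patients from an "ongoing memory-clinic recruited longitudinal cohort of patients with amnestic mild cognitive impairment". AD and LBD patients come from the hospital's memory clinic.
- Section 8.1 calls the study exploratory and says that "there is no data available on the distribution of flow index or vessel density in the population".

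**The concern.** The sample is not a natural population. Its mix of diagnoses is set by design, at 15/15/15/15/15/10. The study itself asks whether OCT values vary with dementia, and recruiting controls from the community and patients from memory clinics makes different risk-factor prevalences plausible. If both differ, a pooled model without group terms can show a link between OCT and a risk factor that is really a difference between diagnoses, or can mask a true link.

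Logistic regression also needs a categorical outcome. Since the sentence does not say which variable that is, one could fear that a continuous OCT value would be cut in two, with no population data to support a cut-point. Section 9 adds that "the trial protocol will be followed rigorously", which might seem to bind the analyst to the bare sentence. At stake is the only named analysis of a stated secondary objective.

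**Working it through.** **Inputs from the protocol.** Group sizes (synopsis and 8.1): 15+15+15+15+15+10 = 85, which matches the stated total. Test level (8.2): two-sided 0.05. The protocol gives no effect size, SD, power or risk-factor prevalence, so every such figure below is an assumption.

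**1. Size of the bias if the model is pooled and unadjusted.** Suppose OCT is shifted by d SD in the 25 dementia patients (15 AD + 10 LBD) and not in the other 60, with no association inside groups. Then

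spurious difference = d × [P(dementia | risk factor) − P(dementia | no risk factor)].

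- Prevalence 30% without and 50% with dementia: 12.5/(12.5+18) − 12.5/(12.5+42) = 0.410 − 0.229 = 0.181 (0.1805 before rounding).
- Prevalence 30% and 60%: 15/(15+18) − 10/(10+42) = 0.455 − 0.192 = 0.262.

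Multiplying by d gives the third column. The last two columns are false-positive rates from 10,000 simulated studies per row; adjusted means five group terms, age and sex.

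| d (SD) | Prevalence | Spurious difference (SD) | Unadjusted logistic | Adjusted logistic |
|---|---|---|---|---|
| 0.5 | 30 vs 50% | 0.09 | 6.4% | 5.6% |
| 0.8 | 30 vs 50% | 0.14 | 8.6% | 5.5% |
| 0.8 | 30 vs 60% | 0.21 | 13.2% | 5.5% |
| 1.0 | 30 vs 50% | 0.18 | 10.6% | 5.3% |
| 1.0 | 30 vs 60% | 0.26 | 18.0% | 5.1% |

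A second simulation placed MCI halfway between controls and dementia (about 2,000 studies per scenario, adjusted for group only, 1 SD shift). Unadjusted against adjusted, it gives 18.4% vs 5.8% when prevalence runs from 30% to 70%, 7.8% vs 5.2% from 40% to 60%, and 4.2% vs 4.0% when prevalence is equal.

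Masking is possible too. With a true 0.5 SD difference and an opposing dementia shift of 0.8 to 1.0 SD, power is 14 to 29% unadjusted against 54% adjusted.

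**2. Does that set-up match the recruitment argument?** Not fully. The argument contrasts community with memory clinic, which is 30 controls against 55 patients, because MCI patients are also memory-clinic recruits. The table splits 60 against 25. Let prevalence differ by recruitment source while OCT still shifts only in dementia:

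- 30% vs 50%: 12.5/(27.5+9) − 12.5/(27.5+21) = 0.342 − 0.258 = 0.085. Times 0.8 SD this is 0.07 SD, against 0.14 above.
- 30% vs 60%: 15/(33+9) − 10/(22+21) = 0.357 − 0.233 = 0.125. Times 1.0 SD this is 0.12 SD, against 0.26 above.

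So the bias roughly halves when prevalence follows the split that section 4.1 actually describes.

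**3. Is the model class at fault?** Power for a true 0.7 SD difference at prevalence 20/30/50%:

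- Linear: 70.4/82.2/88.3%. Logistic with the risk factor as outcome: 68.9/80.9/87.4%.
- Adjusted linear: 66.4/78.5/85.3%. Adjusted logistic: 67.3/79.5/86.3%.
- Logistic with OCT split at its median: 48.7/62.8/71.7%.

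Only the median split does badly, losing 20.2, 18.1 and 15.7 points against logistic with continuous OCT, and no passage proposes it. An objective worded as the presence of risk factors, a history questionnaire, and OCT values summarised by mean and SD all point to a binary risk factor as outcome and continuous OCT as predictor.

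**4. Is adjustment free?** Adjusted logistic has eight slopes (OCT, five group terms, age, sex). At 20% prevalence there are 0.20 × 85 = 17 events, about two per slope, and in simulation the OCT slope drifts from 0.70 to about 0.80. Diagnosis may also lie between vascular risk and retinal change, in which case adjusting for it removes part of the association sought.

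**The case for a change.** The best case for a change is that this is the only analysis named for the objective. The sentence fixes a model class without saying what is modelled, separate fits in groups of 10 to 15 would be so weak that pooling is the natural reading, and one added sentence would settle the outcome and covariates before results are seen. Age strengthens it: if OCT changes 0.3 to 0.4 SD per decade and the risk-factor odds double per decade, unadjusted false positives reach 8.0 to 11.5%. That scenario applies ages 55 to 85 to everyone, though. The protocol gives that range only for the control cohort in 4.1 (55 to 80 in the synopsis) and gives none for patients.

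Two parts of this stand. Pooling without adjustment could mislead, and writing the choice down in advance is good practice. But silence on covariates does not fix an unadjusted model, and following a silent sentence rigorously does not forbid covariates. The place to write it down is the SAP, which was not available for this check. The preference for linear regression does not stand, because adjusted linear and adjusted logistic perform alike.

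**Conclusion.** No change to the protocol follows. The sentence in 8.2 is sparse, but nothing in it is wrong: the model it names is valid and about as powerful as the alternative when the risk factor is the outcome, which is the natural reading. What it omits (outcome coding, covariates, pooling) is commonly settled in a SAP. A sensible analyst would take each risk factor as outcome and OCT as a continuous predictor, account for age, sex and diagnostic group as far as the number of events allows, and show unadjusted estimates alongside, since diagnosis may be a mediator.

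The possible harm ranges from nil (equal prevalence, or no OCT shift) to about 18% false positives at the assumed extreme, and it arises only if the analyst pools without adjusting. Those figures rest on assumed shifts and prevalences that the protocol does not give, and on a 25 against 60 split that about doubles the bias expected when prevalence follows recruitment source. For a secondary association in an exploratory study, this is a gap that analysts fill sensibly.

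### Does one P<0.05 rule for every AUC and regression in section 8.2, with no primary parameter or contrast, call for a change?

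*Protocol*

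**What the plan says.** Section 8.2 plans descriptive statistics and then, for diagnostic performance, ROC "curves with 'area under the curve' (AUC) analysis will be used". The secondary question on vascular risk follows: "Logistic regression models will be used to assess the association between retinal/choroidal vascular parameters and cardiovascular risk factors". The threshold comes next: "Statistical significance will be based on two-sided P-values of <0.05". Nothing is said about adjusting, ordering or labelling the resulting P-values.

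The Endpoints row of the synopsis reads "The diagnostic performance of retinal and choroidal thickness, flow index and vessel density to classify between amyloid positive vs amyloid negative" controls, followed by the same split in MCI, and then AD and DLBD with no comparator given. Section 5, item 6, repeats the list: "to classify between amyloid positive vs amyloid negative controls, amyloid-positive vs amyloid negative MCI, AD and DLBD will be evaluated". Four parameters are named together, and none is singled out.

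On the status of the study, section 8.1 says "This exploratory study is aimed to provide data on the distribution of these parameters in the healthy and diseased population". The synopsis opens its purpose with exploring distributions and adds "and to evaluate the diagnostic value of these parameters". Its primary objective is the relative distribution of the parameters across groups. Diagnostic performance is listed as a secondary objective.

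**The concern.** A flat 5% threshold applied to many AUCs invites someone to pick the best one and call it a marker. The protocol does not close the list of tests, because AD and DLBD have no stated comparator. The only endpoint in the synopsis is diagnostic performance, so a reader could take a significant AUC as the answer to the diagnostic question. Section 8.2 does not repeat the exploratory label that would discourage this.

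Small groups add to the worry, since a just-significant AUC has a wide interval. Both eyes are scanned (section 5, item 4: "OCT: Macula centered cube followed by optic disc centered cube, for both eyes") and section 8.2 does not name the unit of analysis. What would be at stake is a chance finding reported as a promising OCT marker of amyloid status.

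**Working it through.** **The plan's own figure.** The group sizes in section 8.1 give 5 × 15 + 10 = 85, which matches the synopsis. No power or effect size is stated, so nothing else can be reproduced.

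**Inputs.** From the protocol: two-sided alpha 0.05; 4 parameters; 2 contrasts with both sides named (amyloid-positive v amyloid-negative in controls and in MCI), each 15 v 15. Assumed: each AUC is tested against 0.5 (section 8.2 names no null), and the correlation between parameters lies between 0 and 0.8.

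**Chance of any false positive, narrowest reading.** There are 4 × 2 = 8 tests.
- Expected false positives: 8 × 0.05 = 0.40.
- Independent tests: 1 − 0.95^8 = 0.337.
- Simulated Mann-Whitney tests (20,000 null studies, asymptotic P with and without continuity correction):

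| Correlation between parameters | P(at least one P<0.05) |
|---|---|
| 0 | 31–34% |
| 0.5 | 27–29% |
| 0.8 | 20–22% |

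A separate run of 4,000 null studies without continuity correction gave 34%, 29% and 23%. The range is therefore about 20 to 35%. If all 15 pairs of the six groups were tested (60 tests, a reading the protocol does not state), the same run gave 85%, 78% and 65%. No regression is counted in any of these figures.

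**Error of a single test.** In the simulations each test rejected in 4.3–5.0% of null studies. The stated rule does what it says, test by test.

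**What a just-significant AUC means at 15 v 15.**
- Null SE = √[(15+15+1)/(12 × 15 × 15)] = √(31/2700) = 0.107.
- Smallest significant AUC = 0.5 + 1.96 × 0.107 = 0.710.
- Hanley-McNeil SE at 0.71 = 0.0955, so the 95% CI is 0.71 ± 1.96 × 0.0955 = 0.52 to 0.90.

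This width comes from the sample size. It would be the same for one pre-named test, so it is not a consequence of the P-value rule.

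**What strict control would cost.** Bonferroni over 8 tests uses 0.05/8 = 0.00625, with z = 2.73. The smallest significant AUC becomes 0.5 + 2.73 × 0.107 = 0.79. Approximate power at 15 v 15:

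| True AUC | At 0.05 | At 0.00625 |
|---|---|---|
| 0.7 | 46% | 17% |
| 0.8 | 86% | 53% |

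**What Benjamini-Hochberg would buy.** If nothing differs between any groups, it brings the chance of any false positive among the AUCs to 3–4%. That figure holds only under this global null. Take 16 tests, with AD and LBD each also compared with amyloid-negative controls (comparator assumed). If those two groups truly differ by 1 to 1.5 SD (assumed), the chance of at least one false amyloid finding is 7–18%. The method controls the false discovery rate over the whole set, and real differences in dementia relax the threshold for the amyloid tests.

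**The case for a change.** The strongest case for a change is that the protocol commits itself to a decision rule, and that the rule sits uneasily beside a stated aim of judging diagnostic value. Someone following section 8.2 to the letter would report any AUC with P<0.05 as significant. A few sentences would prevent that, at no cost in data or participants. The arithmetic behind this stands: on the narrowest reading, a study with no true signal would still show something significant about one time in three to five. It is also true that the Endpoints row lists diagnostic performance alone, so the ranking of objectives is not perfectly clean.

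The step from there to a fault does not stand. That the P-values are unadjusted is read from silence, and the sentence is compatible with adjusted P-values. No section says that P<0.05 establishes diagnostic value, and the tool named for that question is the ROC curve and its AUC. Exploring distributions and looking at diagnostic value in one small study is no contradiction, and section 8.2 need not repeat a label given in section 8.1. The point about two eyes would matter only if eyes were entered as independent records, which the protocol nowhere says.

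**Conclusion.** No change is needed. The lack of a ranking or adjustment limits how a single significant AUC may be read, by the 20 to 35% given above for the two named pairs. That range rests on a global null, a test of AUC against 0.5, and assumed correlations of 0.8 to 0; any larger figure depends on comparators the protocol does not name. It is not an error in the plan, because the per-test rule is correct, no study-wide rate is claimed and the primary objective is descriptive.

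What remains is detail that an analyst would fill sensibly, or that an analysis plan not seen here may already hold: calling the P-values exploratory, giving each AUC its 95% CI, naming the AD and LBD comparators, and using one value per participant. Error control across the AUCs is a fair trade-off to decline at this size, since Bonferroni would cut power for a true AUC of 0.8 from about 86% to 53%. Benjamini-Hochberg would not reliably protect the amyloid contrasts once the dementia groups differ.
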